Primary objective: To estimate the efficacy, as assessed by the best objective response rate (complete response + partial response) at 24 weeks by RECIST 1.1, of talimogene laherparepvec in combination with pembrolizumab in each sarcoma subtype-specific cohort [(i) UPS/myxofibrosarcoma, (ii) epithelioid sarcoma and (iii) cutaneous angiosarcoma]

Secondary objectives:

1. To assess the safety of talimogene laherparepvec in combination with pembrolizumab in patients with advanced sarcoma using CTCAE v4.03 criteria for toxicity assessment
2. To determine the progression free survival (PFS) rate at 24 weeks by RECIST 1.1 and irRECIST and overall survival (OS) for patients in each sarcoma subtype-specific cohort treated with talimogene laherparepvec in combination with pembrolizumab..
3. To evaluate the efficacy, as assessed by the best objective response rate (complete response + partial response) at 24 weeks by immune-related response criteria (irRECIST), of talimogene laherparepvec in combination with pembrolizumab in each sarcoma-subtype specific cohort.

Additional Cohorts: Exploratory Objectives

Exploratory objectives:

1. To evaluate associations between selected biomarkers measured in serial peripheral blood with clinical efficacy, including immunophenotyping and functional analyses, evaluation of serum levels of chemokines, cytokines and other immune mediators, and characterization of T-cell receptor clonality in peripheral blood.
2. To assess the potential effect of talimogene laherparepvec cell lysis and pembrolizumab on selected biomarker expression measured in pre- and post-treatment tumor tissue and the association between these biomarkers and with clinical outcome, including characterization of PD-1/PD-L1 expression, tumor infiltrating lymphocytes (TILs) and tumor antigens, gene expression profiling, bulk RNA sequencing to define the immune infiltrate, single cell RNA sequencing of TILs, and characterization of T-cell receptor clonality in tumor-infiltrating lymphocytes (TIL).
3. To evaluate the association between baseline tumor mutational burden and neoantigen production with clinical efficacy of the study therapy.
4. To evaluate the potential for noninvasive imaging modalities including photography, confocal microscopy, optical coherence tomography, and ultrasound for the purposes of monitoring and/or predicting response to therapy in patients with cutaneous disease

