Following enrolment of the first 20 patients on this study additional cohorts will open. In the initial 20 patients enrolled on this study, the ORR overall was 35% and the ORR at 24 weeks was 30%. Objective response was observed in 5 histological subtypes including UPS, myxofibrosarcoma, cutaneous angiosarcoma, epithelioid sarcoma and undifferentiated sarcoma not otherwise specified. The additional cohorts will include a total of 40 patients and will be divided into 4 cohorts. Thirty patients with inoperable, locally advanced/metastatic sarcoma will be enrolled onto one of 3 cohorts based on sarcoma-specific subtype [i) UPS/myxofibrosarcoma, ii) epithelioid sarcoma, iii) cutaneous angiosarcoma]. Each cohort will enroll 10 patients. Patients with inoperable, locally advanced/metastatic sarcoma will be treated following the study design as highlighted above.

In the metastatic/locally advanced cohort, patients who achieve a CR or complete disappearance of the injectable lesion may stop intralesional injections of talimogene laherparepvec, but treatment with pembrolizumab will be continued. Study therapy may continue for a total of 35 cycles in the absence of confirmed progression of disease or clinical progression, disappearance of injectable lesions (talimogene laherparepvec only), intercurrent illness that prevents further administration of treatment, or intolerance of study treatment. Patients who discontinue study therapy after a maximum of 35 cycles of study therapy will be allowed to resume study therapy for an additional 17 cycles in the setting of progression of disease off study therapy. In the neoadjuvant setting, TVEC and pembrolizumab will continue for up to 8 cycles prior to surgical resection. On completion of surgery pembrolizumab alone will continue as tolerated for a total of 17 cycles (neoadjuvant and adjuvant therapy). Safety data will be collected for up to 30 days following surgical resection.

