c) Tumor Biopsy gene expression profiling: Fresh tumor biopsy will be examined for RNA gene and protein expression by NanoString technology (nCounter® RNA: Protein, PanCancer Immune Profiling Panel) and/or qRT-PCR to detect expression of immune related genes. This panel includes 770 immune related genes including: 109 genes related to cell surface markers for 24 different immune cell types and populations, 30 genes for commonly studied cancer/testis (CT) antigens, over 500 genes for measuring immune response and 40 reference genes.

d) Neoantigen analysis: Massively parallel sequencing of the whole exome of the tumor tissue and normal blood will be performed for patients who opt in. Genomic DNA will be captured via solution-based hybrid selection and sequenced on the Illumina HiSeq platform by the Genomics Core at MSKCC. The sequencing data will be aligned by the Bioinformatics Core Tumor, using Somatic Sniper, Somatic Indel Detector and Mutect softwares.

- e) **Next generation sequencing for T-cell receptor clonality in tumor-infiltrating lymphocytes (TIL):** Samples will be analyzed using high throughput sequencing of the variable β-chain of the T cell receptor (TCR) to characterize the expansion and clonality of the T-cell repertoire in TILs.
- f) **Tumor Biopsy Analyses:** Tissue microarrays (TMA) will be created using biopsy tissue mounted on poly-L-lysine coverslips, done by central pathology. Deidentified TMAs will be shipped to Enable Medicine for imaging analysis.

Role of Enable Medicine as a Participating Site is as Follows:

- Specimens will be labeled with deidentified study IDs, to only indicate cohort identification and patient subsets.
- Documents will be sent with a simple packing sheet providing an inventory list of the material being sent.
- No participant identifiers will be shared.
- Specimens will be shipped to Enable Medicine, located at [name].
- Specimens will be shipped at ambient temperature.
- Specimens are being tracked in a secure MS Excel that has been locked.
- Specimens should be received during normal business hours, M-F.
- Enable Medicine's primary contact is as follows, and will be notified when shipments go out – and to confirm shipment receipt
 - [name] ([contact])
- Preferred Courier is FedEx

g)

Peripheral blood studies

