14.0 BIOSTATISTICS

14.1 Primary and Secondary Endpoints Statistical Considerations

The primary objective is to evaluate the efficacy, as assessed by the best objective response rate (complete response + partial response) at 24 weeks by RECIST 1.1 (primary endpoint; Phase II). The study will use a one stage design based on the exact binomial test. A 5% response rate will be considered not promising,^{94,95} a 30% response rate will be considered promising. There will be a maximum accrual of 20 patients to this study, with early stopping rules for predefined treatment-related toxicities. . It will be concluded that the true response rate is $> 5\%$ if there are 3 or more patients with an objective response among 20 patients. The design has a type I error rate of 0.08 and a type II error rate of 0.04. This design provides 96% probability of a positive result if the true response rate is at least 30%, and a 92% probability of a negative result if the true response rate is 5% or lower.

The patient population in this study represents patients with locally advanced/metastatic sarcoma that have received at least one line of previous therapy. The references supporting the 5% null rate include the PALETTE, double-blind, randomized placebo-controlled trial⁹⁴ and a study looking at the efficacy of eribulin in patients with advanced

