III. To assess the potential effect of talimogene laherparepvec cell lysis and pembrolizumab on selected biomarker expression measured in pre- and post-treatment tumor tissue and the association between these biomarkers and with clinical outcome, including characterization of PD-1/PD-L1 expression, tumor infiltrating lymphocytes (TILs) and tumor antigens, gene expression profiling, and characterization of T-cell receptor clonality in tumor-infiltrating lymphocytes (TIL). The pre- and post-treatment measurements will be compared using the paired t-test for each of these biomarkers. The associations with the selected biomarkers, in terms of both the pre-treatment measurement and the difference between pre- and post-treatment measurements, will be evaluated using the two-sample t-test for clinical outcome such as response and clinical benefit, and using survival data analysis (including Kaplan-Meier curve and Cox Proportional Hazards models) for survival outcomes such as progression-free survival and survival. More specifically, Kaplan-Meier curve and Cox Proportional Hazards models will be used for analyzing pre-treatment measurement; Kaplan-Meier curve at a landmark time point and Cox Proportional Hazards models allowing for time varying coefficients will be used for analyzing the difference between pre-and post treatment measurements.

IV. To evaluate the association between baseline tumor mutational burden and neoantigen production with clinical efficacy of the study therapy.

The associations with baseline tumor mutational burden and neoantigen production will be evaluated using categorical data analysis (including Fisher's exact test and logistic regression) for clinical outcome such as response and clinical benefit, and using survival data analysis (including Kaplan-Meier curve and Cox Proportional Hazards models) for survival outcomes such as progression-free survival and survival.

V. To evaluate pre and posttreatment magnetic resonance Images of the recurrent, resectable, sarcoma in patients in enrolled in the additional neoadjuvant cohort, to assess for definable radiological changes that can be correlated with treatment response

Summary statistics will be used to for describing changes across time. The associations between radiological changes and treatment response (clinical and pathological) will be evaluated using categorical data analysis (including Fisher's exact test and logistic regression).

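### Objective IV names Fisher's exact test for two quantitative markers without a cut-point, so the result depends on a choice the plan leaves open

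*Combined protocol and SAP*

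**What the plan says.** The aim, in section 2.0, is: "To evaluate the association between baseline tumor mutational burden and neoantigen production with clinical efficacy of the study therapy". Section 14.2, objective IV, gives the analysis: "The associations with baseline tumor mutational burden and neoantigen production will be evaluated using categorical data analysis". For binary outcomes it proceeds "using categorical data analysis (including Fisher's exact test and logistic regression) for clinical outcome such as response and clinical benefit"; for PFS and survival it proceeds "using survival data analysis (including Kaplan-Meier curve and Cox Proportional Hazards models) for survival outcomes". It gives no cut-point, grouping rule, significance level or sidedness, and it does not say whether the two markers enter as continuous or grouped.

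The neighbouring objectives in 14.2 are more explicit. Objective II uses the same phrase about categorical methods, but first says how its markers become categories: time trends are sorted into groups by eye or by clustering. Objective III compares biomarker values between outcome groups with a two-sample t-test, so they stay continuous.

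On numbers, section 14.1 says: "There will be a maximum accrual of 20 patients to this study". Section 4.1 reports: "In the initial 20 patients enrolled on this study, the ORR overall was 35% and the ORR at 24 weeks was 30" per cent. Section 10.3 makes sequencing voluntary: the "whole exome of the tumor tissue and normal blood will be performed for patients who opt in".

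**The concern.** Both markers come from exome sequencing as quantities: a mutation burden and a predicted neoantigen load. Fisher's exact test cannot be run on them until someone decides who is high and who is low. With about six responders, moving one patient across the line can change the conclusion, so the missing rule is not a formality.

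Two things are at stake. A cut fixed in advance at an unlucky place leaves little chance of seeing a real association. A cut chosen once the data are known manufactures associations. Section 14.2 says these analyses should help identify patients likely to benefit and inform later phase III designs, so a spurious or missed signal could be carried forward.

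**Working it through.** **Plan's own figures.** The documents give no operating characteristic for objective IV, so there is none to reproduce. The primary test in 14.1 (at least 3 responses in 20, 5% against 30%) does reproduce: type I error 0.0755 and power 0.9645, against the stated 0.08 and 96%.

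**Inputs from the documents.** 20 patients (14.1). Responders: 30% of 20 = 6 at 24 weeks, 35% of 20 = 7 overall (4.1).

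**Assumptions not in the documents.** All 20 are sequenced; two-sided 0.05 level; marker normal on the log scale with a mean difference of 1.25 SD between responders and non-responders; the cuts shown below.

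**Step 1: Fisher's test at a median split (10 high, 10 low), 6 responders.** There are C(20,6) = 38,760 ways to place the responders.
- 6-0: 2 × C(10,6) / 38,760 = 420 / 38,760 = 0.011.
- 5-1: (420 + 2 × C(10,5) × 10) / 38,760 = (420 + 5,040) / 38,760 = 0.141.

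Only 6-0 (or 0-6) is significant, and the attained size is 1.1%. With 7 responders, C(20,7) = 77,520:
- 7-0: 2 × C(10,7) / 77,520 = 240 / 77,520 = 0.003.
- 6-1: (240 + 2 × C(10,6) × 10) / 77,520 = 4,440 / 77,520 = 0.057.

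**Step 2: other cuts, 6 responders.** Each numerator counts the tables no more probable than the one observed.

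| High group | Split | p |
|---|---|---|
| top 9 | 5-1 | (1,386 + 84 + 462) / 38,760 = 0.0498 |
| top 8 | 5-1 | (672 + 28) / 38,760 = 0.018 |
| top 7 | 5-1 | (273 + 7) / 38,760 = 0.007 |
| top 6 | 4-2 | (1,365 + 84 + 1) / 38,760 = 0.037 |
| top 5 | 4-2 | (525 + 15) / 38,760 = 0.014 |
| top 13 | 6-0 | (1,716 + 273 + 7) / 38,760 = 0.0515 |

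A 5-1 division is therefore non-significant at the median but significant with the top 7, 8 or 9. With the top 13, even 6-0 is not significant.

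**Step 3: power at 1.25 SD (simulation).** Fisher's test: about 27% at the median, 47% with the top 8, 60% with the top 6, 61% with the top 9, and 0% with the top 13. Exact rank-sum on the uncut values: 61%, with attained size about 4%. At 1.5 SD the median split gives 40% against 77% for the rank-sum test.

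**Step 4: cut chosen after seeing the data.** With no true association, taking the smallest Fisher p over every cut from the top 5 to the top 15 gives p<0.05 in 13.9% of simulated data sets.

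**Step 5: sensitivity to the number sequenced.** If 14 were sequenced with 4 responders, a 7/7 split could not reach 0.05: 4-0 gives 2 × C(7,4) / C(14,4) = 70 / 1,001 = 0.070. If all 50 patients were pooled with 15 responders, a 25/25 split would reach it at 12-3 (p=0.012). Both scenarios are assumptions.

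**The case against.** The best defence is that the text does not commit to grouping. The word categorical can be read as describing the outcome (response yes or no), in parallel with survival methods for survival outcomes. Logistic and Cox models, both named, accept continuous predictors, and where the authors do mean to categorise a marker, in objective II, they say so. This stands in part: continuous terms are already permitted. It does not cover Fisher's test, which is named and cannot be run without a cut.

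A reader might infer that the plan prescribes a median split, or that significance always needs every responder on one side. It does neither. The median is only an illustration, and Step 2 shows other cuts where 5-1 or 4-2 suffices.

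A reader might also infer that grouping throws away most of the information, or that Fisher's test would nearly always miss a real association. The figures do not support this. Much of the 34-point gap at the median (61% − 27%) is discreteness: held to roughly a 1% size, the rank-sum test has 35% power, only 8 points above Fisher's. At 2 SD, Fisher's test at the median has about 65% power.

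Nor do the documents say that objective IV is tested separately in each ten-patient subtype cohort. Section 2.0 ties the primary objective to each cohort but not this one, and pooling is not stated either.

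Finally, 14.1 calls the tumour-biopsy correlatives exploratory, and 14.2 says the study is not powered for specific hypotheses. That stands, and it limits how much this matters.

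**Conclusion.** The concern holds in a limited form. Objective IV names a test that needs categories for two quantitative markers, gives no rule for forming them, and departs without explanation from its neighbours. Under the stated assumptions (20 sequenced, 6 responders, two-sided 0.05, normal log-scale marker, 1.25 SD), the choice of cut moves the power of Fisher's test between 0% and about 61%. A rank-sum test gives about 61% with no cut to choose, and a cut picked after the fact raises the false-positive rate to about 14%. Because sequencing is opt-in and the objective also covers the additional cohorts, the actual numbers could be smaller or larger; the missing rule remains either way. Severity is minor: no trial decision rests on this objective.

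**What to change.** In 14.2, objective IV:
- Replace Fisher's test for these two markers with an exact Wilcoxon rank-sum test of responders against non-responders.
- Enter both markers on the log scale as continuous terms in the logistic model, fitted by exact or Firth methods because so few responders make separation likely (on a 6-0 split the ordinary odds ratio is infinite), and in the Cox models.
- Use a median split only to draw the Kaplan-Meier curves.

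If the sponsor prefers groups, the minimum is to fix the cut-point before the marker data are examined. That removes the inflation from choosing a cut but not the dependence of power on where it falls.

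The cost is a few sentences. The data are unchanged and nothing more is collected; results would be reported per unit of log burden (for example, per doubling) rather than as high against low.

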15.0 RESEARCH PARTICIPANT REGISTRATION AND RANDOMIZATION PROCEDURES

15.1 Research Participant Registration

Confirm eligibility as defined in the section entitled Inclusion/Exclusion Criteria. Obtain informed consent, by following procedures defined in section entitled Informed Consent Procedures. During the registration process registering individuals will be required to complete a protocol specific Eligibility Checklist. The individual signing the Eligibility Checklist is confirming whether or not the participant is eligible to enroll in the study. Study staff are responsible for ensuring that all institutional requirements necessary to enroll a participant to the study have been completed. See related Clinical Research Policy and Procedure #401 (Protocol Participant Registration).

15.2 Randomization

The study is a single-arm, non-randomized, phase II clinical trial.

16.0 DATA MANAGEMENT ISSUES

A Clinical Research Coordinator (CRC), Clinical Research Associate (CRA), and a Research Regulatory Associate (RRA) will be assigned to the study. The responsibilities of the Clinical Research Coordinator (CRC), Clinical Research Associate (CRA), and Research Regulatory Associate (RRA) include project compliance, data collection, abstraction and entry, data reporting, regulatory monitoring, problem resolution and prioritization, and coordinate the activities of the protocol study team.

The data collected for this study will be entered into a secure database. Source documentation will be available to support the computerized patient record.

16.0.1 Data

Data: Standardized Case Report Forms (CRFs), directions for use and sign off requirements have been generated for this study. Blank case report forms will be sent to the study staff at each participating site for use. The participating Site PI is responsible for ensuring these forms are completed accurately, legibly and in a timely manner.

Source Documentation: Source documentation refers to original records of observations, clinical findings and evaluations that are subsequently recorded as data. Source documentation should be consistent with data entered into CRFs. Relevant source documentation to be submitted throughout the study includes:

- Baseline measures to assess pre-protocol disease status (ex. CT, MRI)
- Treatment records
- Grade 3-5 toxicities/adverse events not previously submitted with SAE Reports
- Response designation

16.1 Quality Assurance

Weekly registration reports will be generated to monitor patient accruals and completeness of registration data. Routine data quality reports will be generated to assess missing data and inconsistencies. Accrual rates and extent and accuracy of evaluations and follow-up will be monitored periodically throughout the study period and potential problems will be brought to the attention of the study team for discussion and action

Random-sample data quality and protocol compliance audits will be conducted by the study team, at a minimum of two times per year, more frequently if indicated.

16.2 Data and Safety Monitoring

The Data and Safety Monitoring (DSM) Plans at Memorial Sloan-Kettering Cancer Center were approved by the National Cancer Institute in August 2018. The plans address the new policies set forth by the NCI in the document entitled “Policy of the National Cancer Institute for Data and Safety Monitoring of Clinical Trials”.

There are several different mechanisms by which clinical trials are monitored for data, safety and quality. At a departmental/PI level, there exist procedures for quality control by the research team(s). Institutional processes in place for quality assurance include protocol monitoring, compliance and data verification audits, staff education on clinical research QA, and two institutional committees that are responsible for monitoring the activities of our clinical trials programs. The committees: Data and Safety Monitoring Committee (DSMC) for Phase I and II clinical trials, and the Data and Safety Monitoring Board (DSMB) for Phase III clinical trials, report to the Deputy Physician-in-Chief of Clinical Research.

The degree of monitoring required will be determined based on level of risk and documented.

The MSK DSMB monitors phase III trials and the DSMC monitors non-phase III trials. The DSMB/C have oversight over the following trials:

- MSK Investigator-Initiated Trials (IITs; MSK as sponsor)
- External studies where MSK is the data coordinating center
- Low risk studies identified as requiring DSMB/C review

The DSMC will initiate review following the enrollment of the first participant, or by the end of the year one if no accruals, and will continue for the study lifecycle until there are no participants under active therapy and the protocol has closed to accrual. The DSMB will initiate review once the protocol is open to accrual.

Final data sets for publication are required to be locked and stored centrally for potential future access requests from outside entities.

16.3 Regulatory Documentation

Prior to implementing this protocol at MSK, the protocol, informed consent form, HIPAA authorization and any other information pertaining to participants must be approved by the MSK Institutional Review Board/Privacy Board (IRB/PB). There will be one protocol document and each participating site will utilize that document.

Participating sites that are conducting data analysis should submit this protocol to their IRB according to local guidelines. Copies of any site IRB correspondence should be forwarded to MSK.

Participating sites that are conducting data analysis must submit the following documents to MSK before specimens can be shipped to the site:

- Participating Site 1572
- Conflict of Interest forms for Participating Site Investigators on the 1572

Role of Stanford University as the participating site is as follows:

- Data analysis being performed by the site: Diagnosis, Age, Gender, ECOG, Prior therapies, All efficacy response parameters (ORR, DOR, PFS, OS) will be shared with Stanford
- The data will be shared via secure file transfer system
- The data will be shared at the end of the study
- Participant identifiers will not be shared

Role of MD Anderson Cancer Center as the participating site is as follows:

- Data analysis being performed by the site: Computational analysis of any tumor sequencing available and combining it with sequencing data available through MD Anderson cohorts. Also, genomic correlates of response to immunotherapy, histology-specific determinants of response to ICB
- Data will be shared via Secure File Transfer System
- Data will be shared as soon as possible since the study has been completed.
- Participant identifiers will not be shared. Only clinical data and demographics will be shared.

